4.9.7. Columbia Suicide Severity Rating Scale (C-SSRS)

The details of derivation and imputation for C-SSRS is described in Appendix B. The following analyses on C-SSRS measurements will be conducted:

- Descriptive summary of subjects who answered “Yes” to any question 1-12 as well as subjects who had suicidal ideation or suicidal behavior at baseline and at any post-baseline visit. The denominator for baseline summary is the number of subjects who were dosed and had baseline assessment; the denominator for post-baseline summary is the number of subjects who were dosed and had at least one post-baseline assessment for each question.
- Descriptive summary of subjects who had treatment-emergent suicidal ideation, subjects who had new suicidal ideation as well as subjects who had worsening suicidal ideation. The denominator is the number of dosed subjects with both baseline and at least one post-baseline suicidal ideation assessment.
- Descriptive summary of subjects who had treatment-emergent suicidal behavior. The denominator is the number of subjects who answered “No” to all suicidal behavior questions at baseline and had at least one post-baseline suicidal behavior assessment.

Listing of subjects having treatment-emergent suicidal ideation will be provided. Subjects who had new suicidal ideation and subjects who had worsening suicidal ideation will be flagged. The listing will display both baseline and post-baseline Suicidal Ideation Scores for each subject. Listing of subjects having treatment-emergent suicidal behavior will also be provided.

4.10. Pharmacokinetic Endpoints

The PK population will be used for the primary analyses of the PK data. PK summaries/analyses will be displayed for 233AS101 Part C subjects only. For subjects from Part A and B different dosing regimens and different durations make it difficult to pool these subjects.

Values below limit of quantitation (BLQ) are set to half of the lower limit of quantitation (LLOQ, 1 ng/mL) at day 1 pre-dose rather than zero so that geometric means can be calculated. Values that are BLQ at all other visits will also be set to half of LLOQ (1 ng/mL) in calculations.

Both plasma and CSF tofersen concentrations will be listed and summary statistics will be presented for each visit. Listings will present the concentrations with the scheduled (nominal) and actual sampling times (i.e. time from dosing) for each subject at each visit. Differences between scheduled and actual sampling times will also be listed for all subjects. Percentage differences between actual administered dose and nominal dose will also be listed.

Summary statistics will also include both the arithmetic and geometric means with corresponding standard errors, as well as the coefficient of variation. Plots of arithmetic and mean concentrations of tofersen versus time will be provided, including standard error bars on both the linear and semi-log scales. The summaries and plots will be based on scheduled visits/timepoints. At the discretion of the pharmacokineticist and/or biostatistician, samples may be excluded from descriptive statistics if there are large deviations between scheduled and actual sampling days or times, or large deviations between actual dose and nominal dose.

A summary of missing plasma and CSF tofersen concentrations will also be provided for PK population for 233AS101 Part C subjects only.

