11. STUDY TREATMENT USE

11.1. Regimen

11.1.1. Participants Who Have Completed Parts A or B of Study 233AS101

Participants will receive 3 loading doses of BIIB067, approximately 2 weeks apart, during the first 4 weeks, and up to 90 maintenance doses of BIIB067, approximately every 4 weeks, by IT injection.

All participants who were not receiving the 100 mg dose of BIIB067 will be dosed at BIIB067 100 mg at their next scheduled Maintenance Dose Visit.

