16.1. Analysis Population

The safety population is defined as participants who enrolled and have received at least 1 dose of study treatment in the extension study. The analyses of clinical function and safety for 233AS102 will be performed for the safety population. Integrated analyses of 233AS101 and 233AS102 will be performed for the populations defined in 233AS101 protocol for mITT and non-mITT.

For participants from Part C of 233AS101 who enrolled in 233AS102, summaries for clinical function, PK, PD/biomarker endpoints, and safety evaluations will also be presented by disease progression subgroup (i.e., those who met prognostic enrichment criteria for rapid disease progression in 233AS101 Part C [labelled as "enriched" for analyses] and all other eligible participants in 233AS101 Part C [labelled as "other"]). Summaries of data collected during 233AS102 for participants from Part C of 233AS101 will be presented by prior treatment group from 233AS101. Integrated summaries of 233AS101 and 233AS102 will be presented by treatment group during 233AS101 for each of the mITT and non-mITT populations, with some limited summaries for overall intention-to-treat population.

Generally, data for participants from 233AS101 Part C will be analyzed separately from that of participants from Parts A and B, but there may be some analyses where all participants in the extension study will be pooled, particularly for safety summaries. Participants from Parts A and B will generally be pooled together; the data in these participants will mainly be grouped overall rather than by dose level, but there may be limited summaries based on individual dose level. Further details will be provided in the interim and/or final statistical analysis plan.

Some of the analyses specified will be more relevant for integrated efficacy, safety, and immunogenicity plans where data from both 233AS101 and 233AS102 will be pooled.

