16.3.2. Methods of Analysis

Plasma and CSF BIIB067 concentrations will be summarized using descriptive statistics and, where warranted, presented graphically.

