16.6.2.7. Antigenicity/Immunogenicity

Anti-BIIB067 antibody results will be summarized by prior treatment groups for participants from 233AS101 Part C and will also be summarized for participants from 233AS101 Parts A and B.

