16.8. Sample Size Considerations

The sample size for this study is based on the number of the SOD1-ALS participants in Study 233AS101 who consent to participate. Up to 183 participants will be dosed in Study 233AS101.

CONFIDENTIAL

The information contained herein may not be used, disclosed, or published without the written consent of Biogen MA Inc.

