CONFIDENTIAL

The information contained herein may not be used, disclosed, or published without the written consent of Biogen MA Inc.

- First use of permanent assisted ventilation (PAV) for ≥ 22 hours per day for ≥ 7 consecutive days.
- Overall survival

CONFIDENTIAL

The information contained herein may not be used, disclosed, or published without the written consent of Biogen MA Inc.

[REDACTED]

[REDACTED]

[REDACTED]

Section 16.1.2, Methods of Analysis

Now reads:

~~Disease progression~~ **Efficacy** will be measured based on changes in ALSFRS-R, percent predicted SVC, HHD Megascore and individual muscle strength, [REDACTED]. Changes from baseline (using definitions outlined above) will be summarized over time for each of these endpoints. ~~The linear mixed model for repeated measures (MMRM) will be used to assess the slope of change by mutation/progressing group (fast progressing versus non fast progressing) and the treatment received during Study 233AS101. Baseline characteristics at the start of Study 233AS101 may be included as fixed covariates. The slope of ALSFRS-R score change will be estimated using linear MMRM as well as derived using data points from each individual participant for each 48 week period. Categorical analysis of slopes in different ordered categories may also be performed.~~

Rationale: This was done in alignment with Study 233AS101 to allow integrated analyses of the 233AS101 and 233AS102 studies.

This change also affects Section 13.1.5, Handheld Dynamometry.

Section 16.7, Sample Size Consideration

Now reads:

The sample size for this study is based on the number of the SOD1-ALS subjects in Study 233AS101 who consent to participate. Up to ~~144~~ **183** subjects will be dosed in Study 233AS101.

Rationale: The sample size was increased due to an increase in sample size for Part C of Study 233AS101 from 60 to 99 subjects who have an opportunity to enroll in this study.

This change also affects Section 7.1, Study Overview.

CONFIDENTIAL

The information contained herein may not be used, disclosed, or published without the written consent of Biogen MA Inc.

SUMMARY OF MAJOR CHANGES TO THE PROTOCOL

Changes to the protocol are presented chronologically. New text is shown in **bold** type; deleted text is shown with a ~~strikethrough~~.

Section 3, Synopsis

The Synopsis was revised to reflect changes made throughout the protocol.

Section 4, Schedule of Activities for Study 233AS102, Table 1

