4.12. Immunogenicity Data

The immunogenicity population will be used for all analyses of immunogenicity data.

- For immunogenicity, the baseline value is defined as the latest immunogenicity data collected at any time prior to the first dose in 233AS102. If no immunogenicity data are collected immediately prior to the first dose in 233AS102, the baseline value is missing and will be imputed as anti-drug antibody negative for immunogenicity analyses.
- Subjects with at least one confirmed post-treatment positive result will be considered treatment-emergent positive for anti-drug antibodies if their baseline result is negative.
- Subjects where none of the post-treatment samples were positive for anti-drug antibodies will be considered negative regardless of their baseline result.
- For subjects who are confirmed positive at baseline and have at least one post-treatment sample with a ≥ 2 -fold increase in titer will be considered positive for anti-drug antibodies. Subjects that are positive at baseline, with subsequent post-treatment samples titers that are within 2-fold will be considered negative for anti-drug antibodies. If there

are any samples which the lab was able to confirm the screen was ADA positive but could not determine the magnitude of the positive response in time for interim datacut off date these will be considered as being ≥ 2 -fold for the purpose of this analysis.

Number and percentage of subjects who has positive result and negative result at baseline, subjects with any post-baseline positive result and negative result, subjects with any positive ADA will be summarized by prior treatment groups.

In addition, for subjects that are considered anti-drug antibody positive with immunogenicity data, the following may be evaluated:

- o Persistent anti-drug antibody response:
 - More than one positive time point that are ≥ 112 days apart
 - or
 - One or more positive time point, but < 112 days of evaluable data post first positive time point.
- o Transient anti-drug antibody response:
 - A single positive time point, followed by ≥ 112 days results which are all negative.

Or

- Two or more positive data points with < 112 days apart, with later negative samples that are ≥ 112 days apart from the first positive result.

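### SAP 4.12 omits the Parts A/B antibody summary that the protocol requires, if read literally; the Part C-only limit on PK summaries in SAP 4.10 is not listed in SAP Section 5

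*SAP*

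**What the plan says.** **Antibodies.** Protocol 16.6.2.7 requires two summaries: Part C by prior treatment group, and results that "will also be summarized for participants from 233AS101 Parts A and B". SAP 4.12 words the main table as "subjects with any positive ADA will be summarized by prior treatment groups" and repeats the prior-treatment grouping for three further displays. SAP 3.5 defines the immunogenicity population without regard to the part of the parent study.

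**Pharmacokinetics.** Protocol 6.2.1 makes plasma and CSF levels a secondary endpoint. Protocol 16.3.1 defines the PK population across all parts, and 16.3.2 says: "Plasma and CSF BIIB067 concentrations will be summarized using descriptive statistics and, where warranted, presented graphically". SAP 3.5 repeats the all-parts population. SAP 4.10 then says "PK summaries/analyses will be displayed for 233AS101 Part C subjects only" and applies the same limit to the summary of missing concentrations. Its reason is that Parts A/B had differing regimens and durations, which makes pooling difficult.

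**Declared changes.** SAP Section 5 lists two departures from the protocol: moving efficacy, biomarker and one redacted class of endpoints to the integrated analysis, and dropping the enriched/other subgroups. Its visible text mentions neither PK nor antibodies. SAP 6.1 does not mention them either.

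**The concern.** For antibodies, the SAP keeps one half of a two-part protocol requirement. Parts A/B participants were re-exposed after a washout that SAP Section 1 puts at 16 weeks to over 2 years, whereas Part C had no washout. Antibody response on re-exposure is therefore a question that mainly this group can answer, and the protocol asked for it to be summarised.

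For PK, a summary of a secondary endpoint is withdrawn for a whole entry cohort, and the section meant to record such departures does not show it. Protocol 5.5 gives the collection of PK and PD data during dose interruption and resumption as one aim of the dosing intervals, and the group with an interruption is the one left out. SAP 4.11 sends PD and biomarker data to the integrated plan. SAP 4.10 names no such destination for PK.

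**Working it through.** **Antibodies: the passages side by side**

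1. Protocol 16.6.2.7 requires Part C by prior treatment, plus Parts A and B.
2. SAP 3.2, Table 6, has four columns: Part C prior placebo, Part C prior tofersen, Part A+B (all doses) and Total. Only the two Part C columns are defined by prior treatment.
3. SAP 3.2 and 4.1 make presentation by study group the default, with prior treatment added for Part C. Both defaults give way where something else is specified.
4. SAP 4.12 specifies prior treatment groups four times: for positive/negative counts, for persistent/transient response, for hypersensitivity-type AEs in ADA-positive subjects, and for the same AEs in ADA-negative subjects.
5. Where the SAP wants both groupings it says so. SAP 4.2 names prior treatment for Part C and study group for all subjects.

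Read literally, item 4 overrides item 3, and the Part A+B and Total columns disappear from all four displays.

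**PK: does the stated reason compel the restriction?**

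Difficulty in pooling does not rule out a separate summary. Protocol 16.1 says "Participants from Parts A and B will generally be pooled together", with limited dose-level summaries possible. Protocol 11.1.1 says that Parts A/B participants not on 100 mg "will be dosed at BIIB067 100 mg at their next scheduled Maintenance Dose Visit". SAP 4.6 already splits Parts A/B doses into below 100 mg and 100 mg, so samples taken on 100 mg can be identified.

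**Size**

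Inputs: Protocol 16.8, "Up to 183 participants will be dosed in Study 233AS101"; the Version 5 amendment summary, an "increase in sample size for Part C of Study 233AS101 from 60 to 99 subjects"; the Version 4 amendment summary, a total raised from 84 to 144 when Part C was added.

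- Reproducing the plan's figure: 84 + 60 = 144; 144 + (99 − 60) = 183. It agrees.
- Parts A/B: 183 − 99 = 84; 84/183 = 45.9% of planned dosing in the parent study.
- Share of the extension, with rollover a for Parts A/B and c for Part C: 84a / (84a + 99c). The documents give neither rate. The values below are assumptions.

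| a | c | Parts A/B share |
|---|---|---|
| 100% | 100% | 45.9% |
| 75% | 100% | 38.9% |
| 50% | 100% | 29.8% |
| 50% | 75% | 36.1% |
| 100% | 75% | 53.1% |

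**Could later Parts A/B samples simply be merged with Part C?**

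Under simple exponential accumulation, the fraction of steady state after four 28-day intervals (112 days) is 1 − 0.5^(112/h), with half-life h in days.

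- h = 28 (about 1 month, Protocol 5.5, estimated for CNS tissue): 93.8%.
- Monkey plasma, h = 22 to 51 (Protocol 5.3.1.2): 97.1% to 78.2%.
- Monkey CSF, h = 20 to 37 (same section): 97.9% to 87.7%.

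The endpoint is plasma and CSF concentration, so the tissue figure alone does not justify merging.

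**The case against.** The SAP is open about the PK limit. It stands in 4.10 with a reason, and Section 1 describes the varied dosing, long washouts and many discontinuations in Parts A/B. Protocol 16.1 says that Part C will generally be analysed apart from Parts A/B and leaves detail to the SAP. The analyses are descriptive. The listing sentences in 4.10 carry no Part C limit, and one covers all subjects. On antibodies, 4.12 has no Part C-only sentence, unlike 4.10. The population covers all parts, and the default layout would supply a Part A+B column. Protocol 16.1 also refers to integrated immunogenicity plans, which are not available here.

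Most of this stands, and it rules out several stronger readings:

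- A reader might infer that the PK endpoint is dropped for Parts A/B. Only the summaries go; listings remain.
- A reader might call the restriction undeclared. It is missing only from the visible text of Section 5.
- A reader might treat the ADA omission as settled. It follows from the literal wording, but the default rule leaves another reading open.
- A reader might conclude that Parts A/B samples after four 100 mg doses belong with Part C. That rests on a half-life for CNS tissue and does not address the differing durations, which are the other half of the SAP's reason.

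The objection does not remove the mismatch with Protocol 16.6.2.7. Leaving detail to the SAP also does not explain why a withdrawn summary of a secondary endpoint is absent from the list of changes.

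**Conclusion.** The concern holds in two parts of unequal weight.

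The antibody wording is the firmer one. The protocol requires a Parts A/B summary, and 4.12 as written does not ask for it in any of its four displays. Whether the tables will in fact lack the column depends on how a programmer weighs 4.12 against the default, and the SAP should not leave that open for a required safety summary.

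The PK restriction is a real departure from Protocol 16.3, stated with a reason but not recorded in Section 5. It is a reporting gap and does not lose data. Section 5 contains a redaction, so this conclusion rests on its visible text.

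The number affected is the count of Parts A/B participants who rolled over, which the documents do not give. The figure of 84 of 183 is planned dosing in the parent study, and the Part C size behind it appears only in an amendment rationale. A reader might take 46% as the extension's share or as a ceiling. It is neither: the assumed rollover rates above give about 30% to 53%.

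**What to change.** **SAP 4.12.** Replace the prior-treatment wording in all four places with *by study group (Table 6)*. The Part C prior-treatment columns stay, and the Part A+B and Total columns then appear in every ADA table and in both tables of hypersensitivity-type AEs by ADA status. The cost is one phrase and two columns that Table 6 already defines, with no new derivation.

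**SAP 4.10 and Section 5.** Do one of the following:

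- Add an item to Section 5 stating that PK summaries are limited to Part C, with the reason already in 4.10. The cost is one sentence.
- Add a simple Parts A/B summary of plasma and CSF concentrations for samples taken on 100 mg, kept separate from Part C. It uses the existing dose split and scheduled visits and needs no new time origin or steady-state cut-off. The cost is an additional table, with small numbers at late visits and mixed time on 100 mg within a visit, which a footnote should state.

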4.11. Pharmacodynamic Endpoints and Biomarker Endpoints

PD/biomarker endpoints will not be summarized or analyzed for Study 102 alone; these data will be combined with data from 233AS101 and summarized and analyzed based on the ISE SAP.

4.12. Immunogenicity Data

The immunogenicity population will be used for all analyses of immunogenicity data.

- For immunogenicity, the baseline value is defined as the latest immunogenicity data collected at any time prior to the first dose in 233AS102. If no immunogenicity data are collected immediately prior to the first dose in 233AS102, the baseline value is missing and will be imputed as anti-drug antibody negative for immunogenicity analyses.
- Subjects with at least one confirmed post-treatment positive result will be considered treatment-emergent positive for anti-drug antibodies if their baseline result is negative.
- Subjects where none of the post-treatment samples were positive for anti-drug antibodies will be considered negative regardless of their baseline result.
- For subjects who are confirmed positive at baseline and have at least one post-treatment sample with a ≥ 2 -fold increase in titer will be considered positive for anti-drug antibodies. Subjects that are positive at baseline, with subsequent post-treatment samples titers that are within 2-fold will be considered negative for anti-drug antibodies. If there

are any samples which the lab was able to confirm the screen was ADA positive but could not determine the magnitude of the positive response in time for interim datacut off date these will be considered as being ≥ 2 -fold for the purpose of this analysis.

Number and percentage of subjects who has positive result and negative result at baseline, subjects with any post-baseline positive result and negative result, subjects with any positive ADA will be summarized by prior treatment groups.

In addition, for subjects that are considered anti-drug antibody positive with immunogenicity data, the following may be evaluated:

- o Persistent anti-drug antibody response:
 - More than one positive time point that are ≥ 112 days apart
 - or
 - One or more positive time point, but < 112 days of evaluable data post first positive time point.
- o Transient anti-drug antibody response:
 - A single positive time point, followed by ≥ 112 days results which are all negative.

Or

- Two or more positive data points with < 112 days apart, with later negative samples that are ≥ 112 days apart from the first positive result.
- o Caveat: Since the data are only being considered from baseline of 233AS102, a subject who became persistent in 101 will not be accounted for as persistent based on their prior data in 233AS101. Therefore, the subject could be summarized as being transient if there is no change in their titer in 233AS102.
- o If a subject has just one positive postbaseline ADA in 233AS102 at last available assessment at the time of Interim cutoff date and is still ongoing, then this subject will be summarized as transient.

Number and percentage of subjects who have persistent ADA result and transient ADA result will also be summarized by prior treatment groups.

The incidence of AEs selected by anaphylactic reaction SMQ, angioedema SMQ, and hypersensitivity SMQ will also be presented for subjects with at least 1 positive ADA result at post-baseline by prior treatment groups. Percentages will be calculated out of the immunogenicity population.

The incidence of AEs selected by anaphylactic reaction SMQ, angioedema SMQ, and hypersensitivity SMQ will also be presented for subjects with negative ADA result at post-

baseline by prior treatment groups. Percentages will be calculated out of the immunogenicity population.

5. Changes to Planned Analyses

- Analysis of efficacy, [REDACTED] and biomarker endpoints are specified in the Protocol; however, they will not be included in 233AS102 final CSR but will be included under the integrated analyses of 233AS101 and 233AS102. Analyses of efficacy and biomarker endpoints conducted for interim data (July 2021 and January 2022) highlighted the limitations of conducting standalone 233AS102 analyses in these endpoints as outlined in section 1. Based on these learnings, it only makes sense to analyze the longitudinal data from 233AS102 for efficacy and biomarker endpoints as part of an integrated analysis of 233AS101 and 233AS102. The analyses from 233AS102 baseline specified in the protocol will therefore not be appropriate and will not be conducted; analyses from other baseline definitions will be discussed in the ISE SAP.
- Safety evaluations are specified to be presented by disease progression subgroup (i.e. ‘enriched’ vs ‘other’); however, no mITT (“enriched”)/non mITT (“other”) analyses will be conducted in 233AS102 final CSR. Previously the subgroups ‘enriched’/‘other’ were provided in support of the mITT/non mITT populations defined as part of the enrichment strategy in 233AS101 Part C. However, based on the learnings, this was not the optimal way to enrich and to account for disease heterogeneity. The most valid analysis is in the ITT population with adjustment for baseline NfL for efficacy [REDACTED] endpoints. For safety, the most appropriate population is the overall safety population. This approach will also be consistent with ITT principle for efficacy and biomarker data which will be conducted based on the ISE.

6. Summary of Changes from the Previous Version of the SAP

The SAP Version 1.0 to 3.0 were based on interim data cuts (July 2021 and January 2022). This version is the final SAP for final CSR reporting. The details of the changes in previous versions can be found in SAP Version 2.0 and 3.0.

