QTc	interval between the start of the QRS complex and the end of the T wave, corrected for heart rate
QTcF	QTc interval using Fridericia's formula
RBC	red blood cell (count)
RNA	ribonucleic acid
RR	inter-beat
SAE	serious adverse event
SAP	statistical analysis plan
SAS	statistical analysis system
SD	standard deviation
SDTM	standard data tabulation model
SE	standard error
[REDACTED]	[REDACTED]
SOC	system organ class
SOD	superoxide dismutase 1
SVC	slow vital capacity
ULN	upper limit of normal
WBC	white blood cell (count)
WHO	World Health Organization
[REDACTED]	[REDACTED]
[REDACTED]	[REDACTED]

1. Introduction

Study 233AS102 is an extension study of 233AS101 to assess the long-term safety, tolerability, pharmacokinetics, pharmacodynamics, and efficacy of BIIB067 administered to previously treated adults with ALS caused by SOD1 mutation, who have completed Parts A, B, or C of Study 233AS101.

Study 233AS101 is a randomized, double-blind, placebo-controlled, 3-part study to examine the efficacy, safety, tolerability, pharmacokinetics (PK), and pharmacodynamics (PD) of BIIB067, administered by intrathecal bolus injection in subjects with ALS and a confirmed SOD1 mutation.

This statistical analysis plan (SAP) is prepared to describe the final analysis for the closeout clinical study report for 233AS102; separate SAPs exist for 233AS101 Parts A and B, 233AS101 Part C, and integrated analyses across the studies. Prior versions of the SAP for 233AS102 (Versions 1.0 to 3.0) were generated for the purpose of interim analyses based on interim data cuts for the study.

BIIB067 will be referred to as tofersen throughout the rest of the statistical analysis plan.

There are limitations for subjects who enrolled from 233AS101 Parts A and B which impact the interpretability of these subjects in 233AS102:

- Subjects who completed Parts A or B of 233AS101 had a significant washout period ranging from 16 weeks to over 2 years from their last dose of study treatment in 233AS101 to their first dose in 233AS102.
- Dosing paradigms varied substantially across subjects as dose levels in 233AS102 were increased over time as additional doses were deemed to have an acceptable safety profile in 233AS101.
- Many subjects had meaningful disease progression during the washout and exposure to lower doses resulting in a large proportion of discontinuations across studies

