There are also some limitations on statistical analysis for subjects who enrolled into 233AS102 from 233AS101 Part C. Some subjects will be tofersen naïve and others will have received approximately 6 months of tofersen treatment prior to entry in 233AS102.

Analyses of efficacy and biomarker endpoints conducted for interim data (July 2021 and January 2022) highlighted the limitations of conducting standalone 233AS102 analyses in these endpoints as outlined below. Based on these learnings, it only makes sense to analyze the longitudinal data from 233AS102 for efficacy and biomarker endpoints as part of an integrated analysis of 233AS101 and 233AS102:

- In contrast to the prespecified integrated analyses of 233AS101 Part C and 233AS102, the standalone analyses of 233AS102 are based on data selected using post-randomization factors and therefore break the original randomization. On the other hand, the overall ITT analysis with the original 233AS101 Part C baseline provides an objective comparison of the two treatment regimens.

- Rate of progression is variable over time. Comparison of the treatment groups from 233AS102 fails to reflect the overall treatment effect due to early tofersen initiation that is evident in 233AS101 Part C. For example, if rate of progression is faster for the delayed start group in period 1 and then becomes comparable to the early start group, the comparison using only period 2 data would be misleading.
- There are imbalances at baseline of 233AS102, as expected due to the effect of tofersen in 233AS101 Part C, thus confounding interpretation of 233AS102 analyses.
- As described above, incorporation of baseline NfL as a covariate is the most objective mechanism to control for disease heterogeneity at baseline. However, baseline neurofilament in 233AS102 cannot be incorporated as a covariate due to the confounding effect of tofersen administration during 233AS102.

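### SAP 4.12 gives two incompatible ADA baseline rules; read literally, the second overrides a positive 233AS101 result and can turn a stable-titre positive into a treatment-emergent one

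*SAP*

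**What the plan says.** SAP Section 4.12 sets the ADA baseline in two consecutive sentences. The first says that "the baseline value is defined as the latest immunogenicity data collected at any time prior to the first dose in 233AS102". It has no look-back limit, so a 233AS101 result qualifies. The second changes the condition: "If no immunogenicity data are collected immediately prior to the first dose in 233AS102", then "the baseline value is missing and will be imputed as anti-drug antibody negative for immunogenicity analyses".

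Three classification rules use that baseline:

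- Baseline negative: "Subjects with at least one confirmed post-treatment positive result will be considered treatment-emergent positive for anti-drug antibodies if their baseline result is negative".
- Baseline positive with a stable titre: "Subjects that are positive at baseline, with subsequent post-treatment samples titers that are within 2-fold will be considered negative for anti-drug antibodies". A rise of at least 2-fold makes the subject positive.
- No positive after treatment: "Subjects where none of the post-treatment samples were positive for anti-drug antibodies will be considered negative regardless of their baseline result".

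The counts are shown by prior treatment group. Protocol Section 16.6.2.7 also requires a summary for Parts A and B.

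**The concern.** The two sentences cannot both be applied to a subject who has an ADA result from 233AS101 but no sample close to the first 233AS102 dose. The first makes the old result the baseline. The second declares the baseline missing and sets it to negative. If the old result was positive, the second rule replaces a known value with its opposite.

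This matters because the study population is largely pre-exposed. In Part C, one prior-treatment group is tofersen-naive, while "others will have received approximately 6 months of tofersen treatment prior to entry in 233AS102" (SAP Section 1). Most Part A and B subjects will also have had tofersen, with an interval before their first extension dose "ranging from 16 weeks to over 2 years from their last dose of study treatment in 233AS101". Antibodies formed in 233AS101 could therefore be counted as arising in 233AS102, unevenly across the displayed groups. Two programmers could also classify the same subject differently and both cite the SAP.

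**Working it through.** The plan states no figure for this point, so there is none to reproduce. The check is to run the rules, then illustrate the size.

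**Can the situation arise?** Table 1 schedules a pre-dose ADA sample at Day 1 and none at Screening, so a missed Day 1 sample has no substitute within 233AS102. For most Part C subjects, Day 197 of 233AS101 is the 233AS102 baseline visit (SAP Section 2.2). SAP Section 3.3.2 accepts Day 197 data as Day 1 predose data if collected within 48 hours of the first dose; Protocol Section 7.2.2 extends this to the Day 225 visit. A subject is exposed to the problem only when no such sample exists. Delayed entry is possible: Protocol Section 9.1 lets rescreening run to 56 days after Day 169, that is Day 225, which is 225 − 197 = 28 days after Day 197.

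**What do the two rules give?** Take a subject who was positive in 233AS101 and has no sample immediately before the first dose. Rule A is the first sentence; rule B is the second, read literally.

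| After the first 233AS102 dose | Rule A (baseline positive) | Rule B (baseline imputed negative) |
|---|---|---|
| 1. No confirmed positive | Negative | Negative |
| 2. Confirmed positive, titre within 2-fold | Negative | Treatment-emergent positive |
| 3. Confirmed positive, titre up at least 2-fold | Positive, as a baseline positive with a rise | Treatment-emergent positive |

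ADA status changes only in row 2. Row 3 changes the label. The baseline positive and negative counts change in all three rows. No row moves from positive to negative, so the error has one direction. A subject whose latest 233AS101 result was negative has the same baseline under either rule.

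**Which outputs are touched?** The baseline counts, the count of subjects with any positive ADA (taken here to follow the classification rules), and the persistent/transient split, which SAP Section 4.12 makes optional and applies to subjects classed positive. The any-post-baseline-positive count and the hypersensitivity-type adverse-event tables by ADA status depend only on post-baseline results and do not change.

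**How large?** Extra treatment-emergent positives per 100 exposed subjects = 100 × m × p × s, where

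- m = share with no sample immediately before the first dose,
- p = share of those with a positive latest 233AS101 result,
- s = share of those with a later confirmed positive within 2-fold.

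The documents give none of these, so all three are assumptions: m 2% to 20%, p 10% to 60%, s 50% to 100%.

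- Low: 100 × 0.02 × 0.10 × 0.50 = 0.1
- Middle example: 100 × 0.05 × 0.30 × 1.00 = 1.5
- High: 100 × 0.20 × 0.60 × 1.00 = 12

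**The case against.** The best defence is that the first sentence governs and the second is a residual rule for subjects with no prior result at all. That would agree with SAP Section 3.1, which takes the closest non-missing value before the first dose, and with SAP Section 2.2, which draws baseline data from the 233AS101 database where appropriate. It may well be what was meant. But the condition in the second sentence is the absence of a sample immediately before dosing, not the absence of any prior result.

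The over-calling may also be deliberate: the same section treats confirmed positives of undetermined magnitude as at least 2-fold. Nothing says the baseline imputation was chosen for that reason. The section's caveat about 233AS101 history covers only persistent versus transient status.

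Three limits do stand. The summaries are descriptive. Protocol Section 16.1 mentions integrated immunogenicity plans, which are not among the documents and may handle prior history. And the first sentence has a weakness of its own: a very old Part A or B positive used as baseline could hide antibodies that disappeared and later returned at a similar titre.

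Two stronger readings are tempting. One is that every subject without a sample labelled Day 1 is imputed negative; the Day 197 provision rules that out for most of Part C. The other is that 1% to 5% of the prior-tofersen group is mislabelled, from assumed rates of 20% × 5% = 1% to 50% × 10% = 5%. That product omits s, so it is an upper bound under those rates, not an estimate.

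**Conclusion.** The concern holds as an internal contradiction with a definite direction. Applied literally, the second sentence makes a previously positive subject with a stable titre treatment-emergent positive, where the first sentence makes the same subject ADA negative. It can only add positives. It falls mainly, not exclusively, on previously exposed subjects, because a prior-placebo subject could also have had a positive result before 233AS102.

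The size cannot be found from the documents. The range of 0.1 to 12 per 100 exposed subjects rests entirely on the assumed m, p and s. In Part C the number is probably small because Day 197 usually supplies the baseline. A reader might infer a material bias in the comparison of prior treatment groups, or a distorted link between antibodies and adverse events. The documents do not support the first, for want of rates, and the second does not follow, because those tables do not use the baseline. The point should be corrected because the rule is wrong as written and easily repaired, not because a large effect has been shown.

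**What to change.** Replace the second sentence of the baseline rule in SAP Section 4.12 so that:

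- baseline is the latest available ADA result and titre before the first 233AS102 dose, 233AS101 results included, as the first sentence already says;
- negative is imputed only when no prior result exists;
- the tables report, by group, how many baselines were imputed and how many came from an older 233AS101 sample, flagging Part A and B subjects with a long washout;
- a sensitivity summary leaves out both kinds of subject.

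If the word *immediately* is kept anywhere, give it a window; the 48 hours already used for Day 1 predose data is the natural candidate.

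The cost is a short SAP edit, two extra counts and one repeated table. No new data collection is needed, provided the 233AS101 results and titres can be retrieved. The SAP's caveat implies that the ADA history exists, but it does not say whether titres were stored.
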